6.6 Drug logistics and accountability

A drug dispensing log will be completed for each subject. Subjects will receive all study medication dispensed at the baseline visit. At weeks 8 and 16, subjects will be instructed to bring all study drug packaging, including unused study drug and empty packaging, to the investigative site at each study visit. Tablets will be counted for a compliance check and drug accountability. At week 16, unused study drug will be returned to the IDS for destruction.

If a dose of study drug is missed, the subject should take a dose immediately if on the same day. Otherwise, they can resume normal once daily dosing the following day. The dose should not be doubled to make up for a missed dose within the same day.

6.7 Post-study therapy

In case subjects discontinue study drug treatment during this study, further therapy is at the discretion of the investigator.

6.8 Prior and concomitant therapy

A summary of the prohibited prior and concomitant therapy, outlined in the exclusion criteria (Section 5.1.2), is provided in [Table 6-1](#).

Table 6-1 Prohibited prior and concomitant therapy

Therapy	Timeframe
Concomitant use of calcium channel blockers and ARBS are allowed	Stable doses for four weeks prior to randomization
Nitrates or NO donors (such as amyl nitrate) in any form, including topical; phosphodiesterase (PDE) 5 (PDE5) inhibitors (such as sildenafil, tadalafil, vardenafil); and nonspecific PDE inhibitors (theophylline, dipyridamole) are prohibited	Concomitant therapy with study drug
Prostacyclin analogs are not allowed.	Concomitant therapy with study drug
Use of strong inhibitors of CYP 3A4 to include: clarithromycin, itraconazole, cyclosporine, gemfibrozil or other fibrates, niacin, rifampin, digoxin and colchicine.	Concomitant therapy with study drug

7. Procedures and variables

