5.1.2 Exclusion Criteria

Subjects who meet any of the following criteria will be excluded from enrollment in the study:

- Medical and surgical history
 - History of known cardiovascular disease or myocardial infarction
 - History of stroke
 - Diabetes mellitus
- Hepatic-related criteria
 - Hepatic insufficiency classified as Child-Pugh C
 - Elevated liver enzymes > two times normal at screening
- Renal-related criteria
 - Estimated glomerular filtration rate (eGFR) < 30 mL/min/1.73m² (MDRD formula), creatinine > 2.0 mg/dL or history of scleroderma renal crisis at the screening visit
- Known allergy or adverse reaction to atorvastatin or another statin drug
- Laboratory examinations
 - Subjects with elevated CPK (greater than two times normal) at screening.
- Prior and concomitant therapy
 - Concomitant use of calcium channel blockers or angiotensin receptor blockers are allowed, provided the participant has been on a stable dose for four weeks or longer at the time of randomization.
 - Concomitant therapy with prostacyclin analogs.
 - nitrates or NO donors (such as amyl nitrate) in any form, including topical; phosphodiesterase (PDE) 5 (PDE5) inhibitors (such as sildenafil, tadalafil, vardenafil); and nonspecific PDE5 inhibitors (theophylline, dipyridamole)
 - concomitant use of strong inhibitors of CYP 3A4 to include: clarithromycin, protease inhibitors, itraconazole, cyclosporine, gemfibrozil or other fibrates, niacin, rifampin, digoxin.
- Other
 - Pregnant women or breast feeding women

- Women of childbearing potential not willing to use adequate contraception (as defined in the aforementioned inclusion criteria, Section 5.1.1) and not willing to agree to pregnancy testing at weeks 8 and 16.
- Smoking or tobacco use within four weeks of screening.
- Any other condition or therapy that would make the subject unsuitable for this study and will not allow participation for the full planned study period

Note: One re-assessment of laboratory parameters is allowed during the screening phase to re-assess the eligibility of subjects.

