7.5.1.5 Adverse events

7.5.1.6 Expected adverse events, and events of special safety interest

Common expected adverse events include: myalgias/artralgias (> 10%), diarrhea (5-14%), nasopharyngitis (4-13%), and dyspepsia (3-6%).

There are four significant adverse events associated with the use of atorvastatin which include 1) increase in fasting blood glucose in patients with diabetes mellitus; 2) hepatotoxicity; 3) rhabdomyolysis; and 4) the very rare event of immune-mediated necrotizing myopathy. Diabetes mellitus is an exclusion criteria for this study.

In regards to hepatotoxicity, elevated serum transaminases have been reported in as high as 2-3% of patients taking a higher dose of atorvastatin (80 mg once daily), although postmarketing reports of hepatic failure are rare. These will be monitored at baseline, week 8 and week 16. We will discontinue if hepatic enzymes are > three times the upper limit of normal.

Many patients receiving HMG-CoA reductase inhibitors experience myalgias, and this is an expected adverse event. Patients receiving HMG-CoA reductase inhibitors have developed rhabdomyolysis with acute renal failure and/or myopathy. This risk is dose-related and is increased with concurrent use of CYP3A4 inhibitors (eg, clarithromycin, protease inhibitors), fibric acid derivatives (eg, gemfibrozil), or niacin (doses ≥ 1 g/day) (see Drug Interactions), which will be monitored. Serum CPKs will be checked at baseline, week 8 and week 16. We will advise patients not to perform unusual or heavy bouts of exercise in the 24 hours before visits. We will discontinue in any patient in which CPK levels are markedly elevated (> 5 times ULN) or if myopathy is suspected/diagnosed. Patients will be instructed to report unexplained muscle pain, tenderness, weakness, or brown urine. If they develop any of these symptoms, they will return for an interval visit with repeat CPK and exam at that time.

Patients receiving HMB-CoA reductase inhibitors have also been rarely reported to develop an immune-mediated necrotizing myopathy (IMNM). IMNM presents as proximal muscle weakness with elevated CPK levels, which persists despite discontinuation of HMG-CoA reductase inhibitor therapy. Serum CPKs will be checked at baseline, week 8 and week 16. We will discontinue in any patient in which CPK levels are markedly elevated (>5 times ULN) or if myopathy is suspected/diagnosed.

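### Table 6-1 says it summarises the Section 5.1.2 drug exclusions, but the two lists differ on protease inhibitors and colchicine and need to be reconciled

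*Combined protocol and SAP*

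**What the plan says.** Three places in the protocol deal with drugs that interact with atorvastatin.

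- **Section 5.1.2 (Exclusion Criteria)** bars from enrolment anyone with concomitant use of strong CYP 3A4 inhibitors, and says these include "clarithromycin, protease inhibitors, itraconazole, cyclosporine, gemfibrozil or other fibrates, niacin, rifampin, digoxin".
- **Section 6.8, Table 6-1** is introduced with the words "A summary of the prohibited prior and concomitant therapy, outlined in the exclusion criteria (Section 5.1.2), is provided in" the table. Its row on strong CYP 3A4 inhibitors names "clarithromycin, itraconazole, cyclosporine, gemfibrozil or other fibrates, niacin, rifampin, digoxin and colchicine". The timeframe given for that row is "Concomitant therapy with study drug".
- **Section 7.5.1.6 (expected adverse events and events of special safety interest)** says of rhabdomyolysis with acute renal failure and/or myopathy: "This risk is dose-related and is increased with concurrent use of CYP3A4 inhibitors (eg, clarithromycin, protease inhibitors". The same sentence goes on to fibric acid derivatives and to niacin with a dose threshold, points the reader to a Drug Interactions entry, and ends "which will be monitored".

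**The concern.** A table offered as a summary of another section should carry the same entries as that section, and this one does not.

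The two places also do different jobs. Section 5.1.2 decides who may enrol, and the Table 6-1 row governs what may be taken alongside study drug. A drug named in only one of them is treated differently at entry and during treatment, and the protocol gives no sign that this is intended.

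What is at stake is consistent handling of a safety rule. For colchicine, the question is whether a user should be enrolled at all, and what follows if one is. For protease inhibitors, the entry missing from the on-treatment table is one that the protocol's own safety section gives as an example of a drug that raises the risk. Concomitant medications are reviewed at screening, baseline, week 8 and week 16 (Section 7.1.1), so study staff would meet the discrepancy at each of those visits.

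**Working it through.** No arithmetic applies. The check is an entry-by-entry comparison of the three texts.

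| Entry | Section 5.1.2 (entry) | Table 6-1 (with study drug) | Section 7.5.1.6 (safety) |
|---|---|---|---|
| Clarithromycin | named | named | named |
| Protease inhibitors | **named** | **absent** | named |
| Itraconazole | named | named | not named |
| Cyclosporine | named | named | not named |
| Gemfibrozil / other fibrates | named | named | named, as a separate class |
| Niacin | named, no threshold | named, no threshold | named, at 1 g/day or more |
| Rifampin | named | named | not named |
| Digoxin | named | named | not named |
| Colchicine | **absent** | **named** | not named |

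**Count.** Each of the first two lists has eight entries. Seven are shared and stand in the same order. One entry is unique to each list, so there are 7 + 1 + 1 = 9 distinct entries, of which two are in conflict. Colchicine appears nowhere else in the document. Protease inhibitors appear only in Sections 5.1.2 and 7.5.1.6.

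**Colchicine.** Under Section 5.1.2 no named drug exclusion applies. The only provision that could keep a user out is the general one about any other condition or therapy making the subject unsuitable, which is a matter of judgement. Under Table 6-1 the same person is on a named prohibited drug from the first dose.

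**Protease inhibitors.** Under Section 5.1.2 they are barred by name. In Table 6-1 they are not named. A reader can still conclude that they are barred during treatment, in two steps: the row covers strong CYP 3A4 inhibitors as a class, and the table refers back to Section 5.1.2. That conclusion is an inference and not a stated rule.

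**Can the class wording settle both entries?** It helps with protease inhibitors, because Section 7.5.1.6 gives them as an example of CYP3A4 inhibitors. It does not help with colchicine. Section 7.5.1.6 treats CYP3A4 inhibitors, fibric acid derivatives and niacin as three separate groups, while Section 5.1.2 and Table 6-1 place fibrates and niacin under the CYP 3A4 heading. Within this protocol the heading is therefore not a clean class definition, and a reader cannot work out from it whether colchicine is meant to be barred at entry.

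**Monitoring and the niacin threshold.** The relevant words in Section 7.5.1.6 are "eg, clarithromycin, protease inhibitors), fibric acid derivatives (eg, gemfibrozil), or niacin (doses ≥ 1 g/day) (see Drug Interactions), which will be monitored". The closing clause can be read in two ways. If it refers to the drugs, it sits awkwardly beside two lists that prohibit them. If it refers to the risk, it agrees with the next sentence, which schedules CPK checks at baseline, week 8 and week 16. The niacin threshold is a plainer difference, since the two lists name niacin at any dose. The Drug Interactions pointer matches no section in the table of contents.

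**The case against.** The best case on the other side is that this is an incomplete summary with little practical consequence. The table row names a class, its wording need not be exhaustive, and Section 5.1.2 speaks of concomitant use, so its bar on protease inhibitors can be carried through to the treatment period. The general unsuitability clause could deal with colchicine. The protocol also has safeguards: scheduled CPK and transaminase checks, discontinuation triggers, and an extra visit if muscle symptoms appear. The monitoring clause may refer only to the risk, and watching for a drug is in any case compatible with prohibiting it.

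Much of this stands, and it limits the point. It does not remove it: the two lists still differ by name, the unsuitability clause is discretionary, and the safeguards detect harm without saying which drugs are allowed.

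A reader might draw three stronger conclusions that the documents do not support.

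- *That someone who starts a protease inhibitor on study breaks no rule.* The class wording and the reference back to Section 5.1.2 point the other way. The omission is an inconsistency, not permission.
- *That Section 7.5.1.6 openly contradicts the prohibition.* The monitoring clause is ambiguous, so this is at most a tension in wording.
- *That the mismatch will cost participants and widen the confidence interval in Section 8.4.* Section 5.2.1 does not name use of a prohibited drug as a reason for withdrawal; at most it falls under the general non-compliance item. Under Section 7.1.2.5, those who stop after eight weeks or more still have the week 16 procedures, which include EndoPAT. Those who stop earlier do not, but the documents give no basis for saying how many participants, if any, would be affected.

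**Conclusion.** The list mismatch is established from the text and needs no assumption: two of nine distinct entries differ between a section and the table that claims to summarise it. It is wrong as written, as an internal contradiction. It is minor in size but more than clerical, because it leaves an entry rule and an on-treatment rule in disagreement on a safety matter.

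The parts differ in strength. The colchicine conflict is the firmest, since nothing else in the protocol resolves it. The protease inhibitor omission is a gap that can be bridged by inference. The monitoring clause and the niacin threshold are secondary and call for clarification only.

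How often the conflict would arise is unknown, because the documents give no figure for use of either drug in this population. The point has no bearing on the sample size, the type I error rate or the primary analysis. Nothing here says which list, threshold or rule is clinically right.

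**What to change.** Reconcile Section 5.1.2, Table 6-1 and Section 7.5.1.6 to a single list that gives each drug one stated status and says whether that status applies at entry, during treatment or both. Keep the list in one place and have the other two sections cite it. In the same edit, say what the monitoring clause in Section 7.5.1.6 refers to, make the treatment of niacin the same throughout, and give the Drug Interactions pointer a target or remove it. The sponsor's clinicians decide the content of the list.

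The cost is a protocol wording change. Design, sample size and analysis stay as they are.

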7.1 Schedule of procedures

Please refer [7.1.1](#) to for a schedule of evaluations.

7.1.1 Tabulated overview**Schedule of events**

Assessment Window (days)	Screening	Baseline	Week 8 +/- 7	Week 16 +/- 7
Window				
Informed Consent	X			
Complete Medical History	X			
Physical Exam		X		X
Randomization		X		
Concomitant Medications	X	X	X	X
Adverse Events		X	X	X
Urine pregnancy test	X	X	X	X
Liver function tests, Creatinine w/ GFR	X	X	X	X
CPK		X	X	X
Fasting lipid panel, C-reactive protein, C3, C4		X		X
Vascular studies:				
EndoPAT (ischemia and post-NTG)		X		X
Laser Speckle Contrast Imaging (ischemia and post-NTG)		X		X
Brachial FMD (ischemia and post-NTG)		X		X
Questionnaires: RCS, Raynauds and Digital Ulcer VAS	X	X	X	X
Questionnaires: PROMIS and SHAQ	X	X	X	X
Digital Ulcer Count	X	X		X
Biomarker (serum, plasma) and cEPC assessment		X		X
Nitrite Analysis		X		X

* VCAM, ICAM, E-selectin, p-selectin, endothelin-1 (ET-1), VEGF, VEGF), angiotensin -1 and -2, interleukin-2, interleukin-13

7.1.2 Timing of assessments

Screening and baseline visits can occur on the same day.

7.1.2.1 Visit 0 – Screening

Screening evaluations will occur after the subject has provided written informed consent. The following evaluations will be performed and information obtained up to 28 days before randomization and the start of study drug treatment:

- Patient information and obtaining of written informed consent
- Eligibility: Assessment of inclusion and exclusion criteria (see Section 5.1)
- Demographic data, including age, gender and ethnicity.
- Complete medical history
- Liver function tests and creatinine with GFR. Labs obtained as part of routine clinical care up to 28 days prior to screening will be accepted.

7.1.2.2 Visit 1 – Baseline (Day 0, Week 0)

The following assessments will be performed at the Baseline visit (Day 0 of study drug treatment):

- Reconfirmation of eligibility (assessment of inclusion/exclusion criteria; Section 5.1), if performed at separate visits
- Cardiovascular history and assessment or risk factors
- Physical Exam
- Assessment of Raynaud and digital ulcer activity and severity (questionnaire)
- Digital ulcer assessment
- Questionnaires
 - SHAQ
 - PROMISE-29
- Vital signs (blood pressure, heart rate, height, weight).
- Vascular Imaging (to be performed simultaneously)
 - EndoPAT
 - Laser speckle contrast imaging
 - Brachial FMD
- Pregnancy test (urine) for all women of childbearing potential (see Section 7.5.2)
- Blood samples for safety (LFTs, creatinine with GFR, CPK)
- Blood sample for biomarkers
- Blood sample for nitrite analysis

- Recording and assessment of AEs (see Section 7.5.1)
- Concomitant therapy
- Randomization to atorvastatin or placebo (see Section 6)
- Dispense study drug

7.1.2.3 Visit 2: 8 weeks

- Assessment of Raynaud and digital ulcer activity and severity (questionnaire)
- Digital ulcer assessment
- Questionnaires
 - SHAQ
 - PROMISE-29
- Recording and assessment of AEs (see Section 7.5)
- Blood samples for safety (LFTs, CPK)
- Pregnancy test (urine) for all women of childbearing potential (Visit 3 and Visit 5) (see Section 7.5.2)
- Concomitant therapy

7.1.2.4 Visit 3: 16 weeks (end of study)

During the maintenance period of the double-blind treatment period, the following assessments will be performed according to the Schedule of evaluations (Section 7.1.1):

- Physical Exam
- Assessment of Raynaud and digital ulcer activity and severity (questionnaire)
- Digital ulcer assessment
- Questionnaires
 - SHAQ
 - PROMISE-29
- Vital signs (blood pressure, heart rate, height, weight).
- Vascular Imaging (to be performed simultaneously)
 - EndoPAT
 - Laser speckle contrast imaging
 - Brachial FMD
- Pregnancy test (urine) for all women of childbearing potential (see Section 7.5.2)
- Blood samples for safety (LFTs, creatinine with GFR, CPK)
- Blood sample for biomarkers

- Blood sample for nitrite analysis

7.1.2.5 Premature discontinuation of study drug treatment

In the event of premature discontinuation of study drug treatment, subjects must undergo the same procedures as outlined for the Week 16 end of study visit if they have completed 8 weeks or more of therapy. If subjects discontinue prior to 8 weeks of therapy, then they will undergo the same procedures as outlined for Week 8. All subjects who discontinue study drug treatment early will have an additional 30 day safety follow-up visit.

7.2 Population characteristics

7.2.1 Demographic

The following demographic data will be recorded:

- Date of birth (month and year) (age)
- Sex
- Ethnicity

7.2.2 Medical history

Medical history findings (ie, previous diagnoses, diseases or surgeries) meeting all criteria listed below will be collected:

- Pertaining to the study indication and inclusion/exclusion criteria
- Detailed cardiovascular history and risk factors (including family history of cardiovascular events)
- Medical history related to concomitant therapy

7.3 Efficacy

Primary efficacy outcome measure:

- Change in microvascular endothelial function as measured by EndoPAT technology.

Secondary efficacy measures:

- Change in Raynaud and digital ulcer symptom and severity
- Change in microcirculatory flow assessed by laser speckle contrast imaging
- Change in macrovascular function assessed by brachial FMD
- Health related quality of life (SHAQ and PROMIS)
- To assess vascular biomarkers in the sera (VEGF, tPA, sE-Selectin, BFGF, VCAM-1, ICAM)
- To assess EPCs.
- To assess nitrite analysis

7.4 Pharmacokinetics / pharmacodynamics

Pharmacokinetic will not be performed in this study.

7.5 Safety

7.5.1 Adverse events

7.5.1.1 Definitions

Definition of adverse event (AE)

In a clinical study, an AE is any untoward medical occurrence (ie, any unfavorable and unintended sign [including abnormal laboratory findings], symptom or disease) in a patient or clinical investigation subject after providing written informed consent for participation in the study. Therefore, an AE may or may not be temporally or causally associated with the use of a medicinal (investigational) product.

In the following differentiation between medical history and AEs, the term “condition” may include abnormal eg, physical examination findings, symptoms, diseases, laboratory, ECG.

- Conditions that started before signing of informed consent and for which no symptoms or treatment are present until signing of informed consent will be recorded as medical history (eg, seasonal allergy without acute complaints).
- Conditions that started before signing of informed consent and for which symptoms or treatment are present after signing of informed consent, at *unchanged intensity*, will be recorded as medical history (eg, allergic pollinosis).
- Conditions that started or deteriorated after signing of informed consent will be documented as AEs.

Definition of serious adverse event (SAE)

An SAE is classified as any untoward medical occurrence that, at any dose, meets any of the following criteria (a – f):

- a. Results in death
- b. Is life-threatening

The term ‘life-threatening’ in the definition refers to an event in which the subject was at risk of death at the time of the event, it does not refer to an event which hypothetically might have caused death if it were more severe.

- c. Requires inpatient hospitalization or prolongation of existing hospitalization

A hospitalization or prolongation of hospitalization will not be regarded as an SAE if at least one of the following exceptions is met:

- The admission results in a hospital stay of less than 12 hours
- The admission is pre-planned
(ie, elective or scheduled surgery arranged prior to the start of the study)
- The admission is not associated with an AE
(eg, social hospitalization for purposes of respite care).

However, it should be noted that invasive treatment during any hospitalization may fulfill the criterion of ‘medically important’ and as such may be reportable as an SAE dependent on clinical judgment. In addition, where local regulatory authorities specifically require a more stringent definition, the local regulation takes precedence.

- d. Results in persistent or significant disability / incapacity

Disability means a substantial disruption of a person’s ability to conduct normal life’s functions.

- e. Is a congenital anomaly / birth defect

- f. Is another medically important serious event as judged by the investigator

7.5.1.2 Classifications for adverse event assessment

All AEs will be assessed and documented by the investigator according to the categories detailed below.

7.5.1.2.1 Seriousness

For each AE, the seriousness must be determined according to the criteria given in Section 7.5.1.1.

7.5.1.2.2 Intensity

The intensity of an AE is classified according to the following categories:

- Mild
- Moderate
- Severe

Mild is defined as asymptomatic or mild symptoms; intervention not indicated.

Moderate is defined as moderate symptoms present; only minimal intervention indicated.

Severe is defined as severe or medically significant symptoms requiring hospitalization or urgent intervention.

